1) Research design: Quasi-Experimental Design (Non-randomized controlled trial) with experiment and control groups for comparison. Because of ethical considerations on older adults for logistical and economical wise, easy to travel, practical, less budget. Similar studies involving rehabilitation or behavioural interventions in real-world settings have widely used quasi-experimental designs. Studies by MA Handley(2018) and AD Harris (2006) demonstrated reliable outcomes using this approach.

2) Study area: Liaoning Province, China.

3) Study population

i) Reference population: Older adults living in Liaoning.

ii) Source population / sampling pool: Elderly care institutions and rehabilitation centers, Liaoning Province.

iii) Target population: Jinzhou Comprehensive Elderly Care Institution and Rehabilitation Center, Liaoning Province.

iv) Sampling frame: List of members from the two elderly care institution and rehabilitation center; Jinzhou Pension Comprehensive Service Center (JPCSC)), and Jinzhou Rehabilitation Hospital (JRH), Liaoning Province.

4) Subject criteria

Objective No. 1 and 2: To develop and validate the psychomotor rehabilitation nursing plan through content/face validation using the Delphi method.

Inclusion criteria:

- i) Professionals with ≥ 5 years of experience in geriatric care, neurological rehabilitation, cognitive rehabilitation, or psychomotor therapy.
- ii) Academic researchers with publications in related fields.
- iii) Intermediate professional title or above.
- iv) Willingness to participate in multiple Delphi rounds and provide informed feedback.

Exclusion criteria:

- i) Experts without sufficient relevant experience.
- ii) Those unable to commit to the Delphi process.

Objective No. 3: To evaluate the effectiveness of the psychomotor rehabilitation nursing plan in enhancing cognitive function among older adults with mild cognitive impairment. (Experimental and control group)

Inclusion criteria:

- i) Older adults are aged 50 years and above.
- ii) Subjective cognitive complaints from the individual or caregiver.
- iii) Screening for MCI using the Mini-Cog scores between 0-2 (SN Abayomi, 2024).
- iv) Basic language communication, listening, speaking, and understanding skills.

- v) Ability to provide informed consent.

Exclusion criteria:

- i) Diagnosed with severe psychiatric conditions (e.g., schizophrenia, major depressive disorder).

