- ii) It is at the end stage of important functional organ diseases, such as malignant tumors, cardiac failure, etc.
- iii) Limb dysfunction.
- iv) Diagnosed with dementia.

Withdrawal criteria:

- i) Withdrawal of consent by the participant.
- ii) Non-compliance with study requirements (e.g., missing >25% sessions).
- iii) Significant health deterioration affecting participation.

5) Study groups

Experimental group: Older adults with MCI from Jinzhou Rehabilitation Hospital (JRH), with psychomotor rehabilitation nursing plan.

Control group: Older adults with MCI from Jinzhou Pension Comprehensive Service Center (JPCSC), without psychomotor rehabilitation nursing plan.

6) Operational definition:

- i) Mild cognitive impairment (MCI): Mild Cognitive Impairment (MCI) is defined as a condition characterized by noticeable cognitive decline beyond what is expected for an individual's age and education level, but not severe enough to interfere significantly with daily life or independent functioning. It serves as an intermediate stage between normal aging and dementia. (Petersen, R.C., 2004; B. Winblad, 2004).
- ii) Psychomotor therapy (PMT): Psychomotor therapy is a form of therapeutic intervention that focuses on the connection between psychological and motor (physical) functions (Duan Zhouying, Chen Wenhua, 2021).

7) Sample size determination

Objective No. 1 and 2: To develop and validate the psychomotor rehabilitation nursing plan through content/face validation using the Delphi method for older adults with mild cognitive impairment in promoting cognitive function.

A sample size of 8 to 15 respondents has been recommended for Delphi studies, given that smaller samples reduce reliability and bigger ones do not appear to add much value (Kenney et al., 2010). For this study, we aimed to recruit 10-12 participants.

Objective No. 3: To determine the effectiveness of the psychomotor rehabilitation nursing plan in enhancing cognitive function among older adults with mild cognitive impairment .

The sample size was calculated for specific objective 2. It was estimated by using the sample size formula compared with the average of two samples (Ni Ping et al., 2010) . The sample size calculation formula and parameters were as below:

$$N1 = N2 = 2[(t_{\alpha/2} + t_{\beta})S/\delta]^2$$

N1 is the sample content of the experimental group.

N2 is the sample content of the control group.

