S is the estimated value of the standard deviation between the two populations.

δ is the difference between the two averages.

The S and δ were the values of the MMSE scale decided by the researcher based on expert opinion (Liang Jingzhao, Zhi Yanmin, 2022), S= 2.75 , δ = 2.14. The level of significance (α) was 0.05, $t_{0.05/2}= 1.96$, β was 0.10, $t_{0.1}= 1.28$. By substituting the formula, 34 samples were required for each of the two groups.

An estimated 10% was added to the calculated sample size in anticipation of some missing data. The calculated sample size for this study was 76 patients (EG: 38 patients, CG: 38 patients).

8) Sampling method: Purposive sampling

9) Subject setting and participant

PHASE 1 (Delphi-method study for screening and recruitment)

The psychomotor rehabilitation nursing plan design will use Delphi-method which is an integration involving multiple expertise for the PMT development. The participants are the professionals with academic and/or practical experience in Neurology and cognitive training in China's hospitals or universities. There is no agreed method to consider someone an expert in a given field. To facilitate the selection process, it will use a simple point evaluation system. It will include all professionals with a final evaluation of at least 2 points. Regarding academic experience, it will consider the following factors: At least one publication on the

field of cognitive training (1 point) & at least one publication on the field of Neurology (1 point) OR at least one publication on the field of cognitive training in MCI (2 points). Concerning practical experience, it will consider experience in the development of a cognitive training program (1 point). Moreover, it will also consider if the professional had clinical experience in the application of cognitive training (1 point).

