Purposive sampling. Potential participants will be identified through a literature review, existing academic contacts, and a web search for cognitive training programs (for MCI or Neurology or other conditions) and the respective scientific teams. After being evaluated in accordance to the point system previously described, professionals who met the inclusion criteria (2 points or more) will be invited to participate by email. In the initial questionnaire, they will be asked to recommend other professionals who they considered to be experts in the field. Recommended professionals who met the inclusion criteria will be contacted and invited to join the expert panel.

PHASE 2 (Quasi-Experimental design for PMT rehabilitation nursing interventional study)

This experimental method will be used in Quasi-Experimental Design (Non-randomized controlled trial) with experiment and control groups for comparison. Ethics consideration on older adults which would psychologically and emotionally impact in case not selected for experimental group. This research will be carried out in Liaoning Province of China. The rehabilitation nursing intervention will be carried out for older adults with MCI admitted in two China elderly care institutions which the name is Jinzhou Pension Comprehensive Service Center (JPCSC) and Jinzhou Rehabilitation Hospital (JRH). Because of ethical consideration on older adults for logistical and economical wise, easy to travel, practical, less budget. So the experimental group is JRH, and the control group is JPCSC. Purposive sampling, whereby older adults with MCI will be selected and invited to participate the study.

The PMT rehabilitation nursing intervention plan

From Table in the literature review, we can see that most interventions lasted for 3 months. Therefore, older adults will be engaged in a 12-week PMT rehabilitation nursing plan involving 2 phases of relaxation and breathing exercises, face exercises, hand exercises and mind exercises to promote cognitive health. The experimental group will be given interventions, twice a week every Tuesday and Thursday 9-10 am along with the study

intervention. Meanwhile, the control group will be given a standard health education on cognitive health.

Table The Mind-body Exercise of Psychomotor Rehabilitation Nursing Plan

Week	Phase	Intervention methods	Assessment

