2.6 Phase 2 -Task 1	Do relaxation and breathing exercises before and after exercise (10 minutes).			
2.7 Phase 2 -Task 2	Hand muscle training/flexibility training/hand-eye coordination/improved circulation: The older adults held and rotated two balls with one hand according to instructions (10 minutes).			
2.8 Phase 2 -Task 3	Hand fine training/flexibility training/hand-eye coordination/endurance and concentration training (10 minutes).			
2.9 Phase 2 -Task 4	Hand-eye coordination training/cognitive ability training/fine skills training/teamwork and social interaction training (10 minutes).			
2.10 Phase 2 -Task 5	Carry out upper limb gymnastics exercises with music to improve limb motor function (20 minutes).			

Objective No. 3: To evaluate the effectiveness of psychomotor rehabilitation nursing plan in enhancing cognitive function among older adults with mild cognitive impairment.

Data entry and analysis will be performed using SPSS 28.0 software. Descriptive statistics will be used to summarize the general information of older adults. Numerical data will be presented as mean (SD) or median (IQR) based on their normality distribution. Categorical data will be presented as frequency (%). The comparison of scores of various scales are based on paired t-test statistical methods. The P value <0.05 will be considered to indicate statistically significant with 95% confidence interval (CI).

Expected result (Dummy Table): The effect assessment of the PMT rehabilitation nursing plan

Table Comparison of cognitive status between two groups ($\bar{x} \pm s$, scores)

Assessment	Before (n = 76)	After (n = 76)	Diff (95% CI)	t	P
Orientation					
Registration					
Attention and Calculation					
Recall					
Language and Praxis					
MoCA total score					

[figure not shown]
Table Comparison of psychological status between two groups ($\bar{x} \pm s$, scores)

Assessment	Before (n = 76)	After (n = 76)	Diff (95% CI)	t	P
Positive scale					
General psychopathology scale					
Negative scale					

Table Comparison of mental rehabilitation status between two groups ($\bar{x} \pm s$, scores)

Assessment	Before (n = 76)	After (n = 76)	Diff (95% CI)	t	P
Mood-related signs					
Behavioral disturbance					
Cyclic functions					
Ideational disturbance					

Study flowchart

Gantt chart & milestone

Research Activities	2024				2025				2026			
	Jan-Mar	Apr-Jun	Jul-Sep	Oct-Dec	Jan-Mar	Apr-Jun	Jul-Sep	Oct-Dec	Jan-Mar	Apr-Jun	Jul-Sep	Oct-Dec
Preliminary discussion												

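### One institution per arm, but the 90% power and the 95% CI are set as if participants were independent

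*Combined protocol and SAP*

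**What the plan says.** Section 1 describes a non-randomised two-group design. Sections 5 and 9 (Phase 2) make the institution the unit of assignment: "So the experimental group is JRH, and the control group is JPCSC". The intervention has one fixed timetable: "The experimental group will be given interventions, twice a week every Tuesday and Thursday 9-10 am".

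For Objective 3, section 7 uses the standard formula for comparing two means: "It was estimated by using the sample size formula compared with the average of two samples". The inputs are "S= 2.75 , δ = 2.14" (MMSE values), alpha 0.05 two-sided and beta 0.10. The result is given as "By substituting the formula, 34 samples were required for each of the two groups", raised by 10% for missing data to 38 per group, 76 in all.

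For Objective 3, section 11 names a paired t-test and this criterion: "The P value <0.05 will be considered to indicate statistically significant with 95% confidence interval (CI"). The dummy table titles announce a comparison between two groups, but the columns are Before and After with n = 76 in each.

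Neither section mentions an ICC, a design effect, a cluster term or any limitation arising from having one institution per arm.

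**The concern.** People in one institution share staff, routine, case mix and, in the experimental arm, a training timetable. Their scores, or their changes in score, may resemble each other more than those of people drawn from different places. The section 7 formula and any person-level test assume that they do not.

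If they do, two statements in the plan fail. The trial does not have the 90% power claimed, and a person-level 95% CI for the difference between groups covers the PMT effect less than 95% of the time. A two-sample t-test or ANCOVA in place of the paired t-test would not cure this, since both also assume independence. With one institution per arm there are no degrees of freedom left to estimate between-institution variance, so the trial's own data cannot supply the correction.

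**Working it through.** **Inputs from the plan (section 7).** S = 2.75, delta = 2.14, 1.96 for two-sided alpha 0.05, 1.28 for beta 0.10, and 34 per group before and 38 after the 10% allowance.

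**Input not in the plan.** The ICC. It is assumed, with an illustrative range of 0.01 to 0.10.

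**Step 1: reproduce the plan's figure.** 2 × [(1.96 + 1.28) × 2.75 / 2.14]² = 34.67. The plan prints 34; adding 10% gives 38. Under independence, with a normal approximation, power is 89.4% at 34 per group and 92.4% at 38.

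**Step 2: power of a test corrected for a known ICC.** With all n people of an arm in one institution, the design effect is DE = 1 + (n − 1) × ICC. The standard error is 2.75 × sqrt(2 × DE / n), and power is Phi(2.14 / SE − 1.96).

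| ICC | DE, n = 34 | Power, n = 34 | DE, n = 38 | n / DE, n = 38 | Power, n = 38 |
|---|---|---|---|---|---|
| 0 | 1.00 | 89% | 1.00 | 38 | 92% |
| 0.01 | 1.33 | 79% | 1.37 | 27.7 | 83% |
| 0.05 | 2.65 | 50% | 2.85 | 13.3 | 52% |
| 0.10 | 4.30 | 34% | 4.70 | 8.1 | 35% |

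Example, n = 38 and ICC 0.05: SE = 2.75 × sqrt(2 × 2.85 / 38) = 1.065; 2.14 / 1.065 − 1.96 = 0.05; power 52%. These are upper bounds, because the ICC is treated as known and this trial cannot estimate it.

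**Step 3: how much ICC the stated power tolerates.** At 34 per group there is no room: power is already slightly under 90% and any positive ICC lowers it. At 38, the design effect may reach 38 / 34.67 = 1.096, so ICC may reach 0.096 / 37, about 0.0026. More people at the same two sites help only up to a point. As n grows, SE falls no further than 2.75 × sqrt(2 × ICC), so 90% power is out of reach at any n once ICC exceeds (2.14 / (3.24 × 2.75))² / 2, about 0.029.

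**Step 4: the uncorrected two-sample test, a different test from step 2.** Trials of 38 per group were simulated with one random institution effect per arm and total SD 2.75.

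| ICC | False positives, both arms correlated | False positives, experimental arm only |
|---|---|---|
| 0 | 5% | 5% |
| 0.01 | 9-10% | 7% |
| 0.05 | 25% | 16% |
| 0.10 | 38-39% | 25% |

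CI coverage is 100% minus these rates, so about 75% at ICC 0.05 with both arms correlated. This uncorrected test keeps simulated power of about 89%, 81% and 77% at ICC 0.01, 0.05 and 0.10, but it does so by exceeding its nominal error rate.

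**Step 5: interval width at 38 per group.** The uncorrected half-width is 1.96 × 0.631 = 1.24 points. Multiplied by sqrt(DE) = 1.17, 1.69 and 2.17, it becomes 1.45, 2.09 and 2.68 at ICC 0.01, 0.05 and 0.10.

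**The case against.** **The planned test is paired.** In a before-after comparison a stable difference between the sites cancels, so the relevant ICC is that of change: shared sessions, staff, and site-by-time effects. This stands. The false-positive rates in step 4 belong to a two-sample comparison and should not be read as those of the paired t-test. The paired test still treats each person's change as independent, however, and section 7 claims power for a two-group comparison, so that claim has to be judged on that comparison. The mismatch between the paired test and the table titles is a separate matter.

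**Conditional on these two sites, an institution difference is bias.** Section 3 names Jinzhou institutions as the target population. A wider standard error does not remove bias, and treating institutions as random is a modelling choice. This also stands. It is why the fix limits the conclusion to these two institutions and does not present the wider interval as a cure.

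**No ICC is given.** True, and the results move a great deal over the assumed range. That supports showing a range. It does not support making an effectiveness claim depend on one guessed value such as 0.05, where the half-width of 2.09 almost equals delta. The documents give no basis for such a rule.

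**One training group is not stated.** A reader might infer from the shared Tuesday and Thursday slot, and from a draft Phase 2 task that lists teamwork among its aims, that all 38 train together. The documents give a timetable, not a group size, and the task is still subject to the Delphi rounds. The point rests on assignment by institution, which is explicit.

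**Conclusion.** The point holds. The 90% power in section 7 is valid only for independent participants, and a person-level between-group 95% CI undercovers for any positive ICC. Corrected power over ICC 0.01 to 0.10 runs from about 79% to 34% at 34 per group, and from 83% to 35% at 38.

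This rests on an assumed ICC (that of change, if change is analysed), on S and delta carried over from MMSE although the trial measures MoCA, and on institutions treated as random.

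Two stronger readings should be avoided. A reader might combine the 52% power and the 25% false-positive rate at ICC 0.05 into one test. No test has both: the first belongs to a corrected test and the second to the uncorrected one. A reader might also conclude that any correlation at all breaks the 90% power. If all 38 per group are analysed, it survives up to ICC of about 0.0026, although coverage is already below 95%.

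**What to change.** Keep 38 per group.

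1. In section 7, state that the 90% power assumes independent participants. Give the corrected power at 34 and 38 per group for ICC 0.01, 0.05 and 0.10 (79 / 50 / 34% and 83 / 52 / 35%). Label the ICC values illustrative and the powers upper bounds, because the ICC cannot be estimated with one institution per arm.

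2. In section 11, name the between-group comparison that the sample size and table titles intend. Beside its person-level CI, report as a sensitivity analysis the CI with the standard error multiplied by sqrt(1 + (n − 1) × ICC) over the same range, using the ICC of change if change is analysed. State that between-institution variance cannot be estimated and that the result is a difference between these two institutions. Attach no binding decision rule to any single assumed ICC.

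The cost is some wording and a few lines of arithmetic, with no extra participants, visits or staff. The downsides are a less favourable stated power, wider sensitivity intervals, and an ICC that has to be assumed.

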rehabilitation nursing program will be modified, deleted and supplemented based on the experts' scores and opinions on the items, so as to determine the second round of expert inquiry questionnaires and conduct the second round of expert inquiry. There will be a 3-week interval between the first and second rounds. After receiving the questionnaires from the experts, the inquiry results will be summarized and statistically analyzed until the experts' opinions reach a consensus, and the entire inquiry process will be terminated.

The duration of participant involvement in the Delphi method will be approximately 6 – 10 weeks in total, depending on the number of rounds required to reach expert consensus. Each Delphi round will require participants to complete the questionnaire, which is estimated to take 20 – 30 minutes per round. Between rounds, there will be a 1 – 2-week interval for data analysis and feedback preparation. While we anticipate achieving consensus within two rounds, a third or fourth round may be necessary if the responses require further refinement. In such a case, participants will be informed in advance, and their continued involvement will be requested. We will strive to minimize the burden on participants while ensuring robust and reliable results.

Phase 2: To evaluate the effectiveness of the psychomotor rehabilitation nursing plan among older adults with mild cognitive impairment.

The data will be collected from January 2025 to December 2025 in China's older adults care institutions. The data collection form was created by the researcher to record general information about older adults, such as age, gender, education level, family history of dementia, marital status, personal annual income, chronic disease. It will take no more than 5 minutes. Then, It will conduct questionnaire surveys before the intervention (baseline) and after the intervention (12 weeks). The questionnaires involved include MoCA, which has 11 questions and takes about 10 minutes; PANSS, which has 30 questions and takes about 20 minutes; HAMA-14, which has 14 questions and takes about 10 minutes; HAMD-17, which has 17 questions and takes about 15 minutes. All questionnaires will take no more than 60 minutes. Due to ethical issues, the names of the elderly participating in this study are only used for data collection, and their identity information will not be disclosed.

Data/Specimen handling:

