1. Collection: Participant data will be collected through questionnaires and assessments during the study. No biological specimens will be collected as part of this research.

2. Storage and Security: All participant data will be anonymized and stored in a password-protected electronic database. Hard copies, if any, will be kept in a locked cabinet accessible only to the research team.
3. Usage: The data will be used exclusively for this study to evaluate the effectiveness of the psychomotor rehabilitation nursing plan. No secondary use of data will occur without additional consent from participants.
4. Retention and Destruction: Data will be retained for 5 years following the publication of the study findings, after which it will be securely destroyed by permanent deletion of digital files and shredding of hard copies.
5. Confidentiality: Participant confidentiality will be strictly maintained throughout the study. All identifiers will be replaced with unique codes to ensure privacy."

Research material: The materials used in PMT rehabilitation nursing intervention plan.

- i) Rehabilitation functional training hand coordinator
- ii) Rehabilitation training geometric figure cognitive plug-in board
- iii) Hand-eye-brain coordination training ball
- iv) Finger Function Dexterity Trainer
- v) Intelligence training puzzle board
- vi) Music for upper limb gymnastics exercises

1) Rehabilitation functional training hand coordinator

2) Rehabilitation training geometric figure cognitive plug-in board

3) Hand-eye-brain coordination training ball

4) Finger Function Dexterity Trainer

5) Intelligence training puzzle board

Questionnaire:

- i) Cognitive assessment:

The cognitive status of older adults was assessed by the Montreal Cognitive Assessment (MoCA) scale. Developed by Nasreddine et al. in Canada with reference to the MMSE, the MoCA evaluates multiple cognitive domains, including attention, executive function, memory, language, visuospatial skills, abstract thinking, calculation, and orientation, making it suitable for a comprehensive assessment of various types of cognitive impairment (Nasreddine ZS, 2005). In Western countries, a cutoff score of 26 is commonly used to identify MCI.

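### The only test named for Objective 3, a paired t-test, does not compare the two groups, and the stated 90% power belongs to a two-group MMSE comparison that the trial will not make

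*Combined protocol and SAP*

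**What the plan says.** **Design.** Sections 1 and 5 describe a non-randomised trial with an experimental and a control group, each drawn from one institution.

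**Sample size.** In section 7, under Objective No. 3, "It was estimated by using the sample size formula compared with the average of two samples", with N1 the experimental and N2 the control group. S = 2.75 and δ = 2.14 "were the values of the MMSE scale decided by the researcher based on expert opinion", with a citation to a study whose title in the reference list concerns senile dementia patients. With α = 0.05 and β = 0.10, "By substituting the formula, 34 samples were required for each of the two groups"; adding 10% gives 38 per group, 76 in all. The section also states, under the Objective No. 3 heading: "The sample size was calculated for specific objective 2".

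**Outcome.** In section 10, Phase 2: "The questionnaires involved include MoCA, which has 11 questions and takes about 10 minutes". The others are PANSS, HAMA-14 and HAMD-17, all given at baseline and at 12 weeks. Under Questionnaire: "The cognitive status of older adults was assessed by the Montreal Cognitive Assessment (MoCA) scale". The MMSE is not in the battery, and no MoCA SD, MoCA target difference or conversion from MMSE is given.

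**Analysis.** The opening summary and section 11 (Objective No. 3) both base the comparison of scale scores on paired t-tests and name no other test. The dummy tables are titled as comparisons of the two groups, but their columns are Before and After with n = 76 each, a difference, t and P. There is no group column.

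**The concern.** The design and the sample size concern a difference between groups. The named test concerns a change over time. Any improvement shared by both groups, from repeating the same scales or from the health education given to controls, counts towards a significant paired result. Objective 3 could then be declared met although the two groups did not differ.

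The power statement has a separate weakness. Section 7 gives the only justification for 76 participants, and it refers to a scale that is not collected and a test that is not named. A reader cannot tell what MoCA difference the trial can detect, or by which analysis.

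**Working it through.** **1. The plan's own figure (inputs from section 7).**
2 × [(1.96 + 1.28) × 2.75 / 2.14]² = 2 × (4.1636)² = 34.67 per group. The plan reports 34; strict rounding up gives 35, which is immaterial. Then 34 × 1.10 = 37.4, so 38 per group and 76 in total. The figure reproduces.
The standardised difference is 2.14 / 2.75 = 0.778. Two-sample t-test power (noncentral t, noncentrality 0.778 × √(n/2)) is 88.5% at n = 34 and 91.7% at n = 38.

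**2. What was sized against what will be analysed.**

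| | Section 7 | Sections 10 and 11 |
|---|---|---|
| Scale | MMSE | MoCA |
| Contrast | experimental v control mean | before v after |
| Test | two independent means | paired t-test |
| n shown | 34 (38) per group | 76 before, 76 after |

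**3. The paired test when the groups do not differ.** The documents give no MoCA SD or correlation. Assume both groups gain 1.0 point, SD 3.0 at each visit, and correlation r between baseline and week 12. The SD of change is 3.0 × √(2(1 − r)), and the noncentrality is 1.0 × √n / SD of change.

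| r | SD of change | Significant, pooled n = 76 | Significant, one arm n = 38 |
|---|---|---|---|
| 0.5 | 3.00 | 82% | 52% |
| 0.6 | 2.68 | 89% | 61% |
| 0.7 | 2.32 | 96% | 73% |
| 0.8 | 1.90 | 99% | 89% |

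**4. What 34 evaluable per group can detect on MoCA.** For 90% power at two-sided 5%, the standardised difference is 0.798 (t, 66 df; also 0.798 at the 65 df of ANCOVA). So the detectable difference is 0.80 × SD unadjusted, and 0.80 × SD × √(1 − r²) with baseline adjustment. The multiplier at r = 0.5 / 0.6 / 0.7 / 0.8 is 0.69 / 0.64 / 0.57 / 0.48. In points, for assumed SDs, with power for 2.14 points beside them:

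| SD | Detectable, unadjusted | Detectable, ANCOVA r = 0.5 | Detectable, ANCOVA r = 0.8 | Power for 2.14, unadjusted | Power for 2.14, ANCOVA r = 0.5 |
|---|---|---|---|---|---|
| 2.5 | 2.0 | 1.7 | 1.2 | 94% | 98% |
| 3.0 | 2.4 | 2.1 | 1.4 | 83% | 92% |
| 3.5 | 2.8 | 2.4 | 1.7 | 70% | 82% |
| 4.0 | 3.2 | 2.8 | 1.9 | 58% | 71% |

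Unadjusted, 2.14 points has 90% power up to an SD of 2.14 / 0.798 = 2.68. Power falls on both sides of 90%. The 2.14 in the last two columns is the MMSE value carried over, itself an assumption.

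**5. Baseline imbalance between institutions.** If they differ at baseline by D within-group SDs, the ANCOVA standard error, and so the detectable difference, is multiplied by √[(2/34 + D²/66) / (2/34)]: 1.03 at D = 0.5 and 1.12 at D = 1.0.

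**The case against.** **The MMSE may be a fair proxy.** The formula depends only on δ/S, and the Questionnaire section says MoCA was developed with reference to the MMSE. If 0.778 carries over, power is 88.5 to 91.7%, essentially as planned. That stands as a possibility, but the plan neither calls the values a proxy nor gives a reason to expect the ratio to hold.

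**The paired tests may be meant within each arm.** The table titles leave room for this, and the chance of a significant result in an arm is then 52 to 89%; 82 to 99% applies only to pooling. Under either reading, no difference between groups is tested.

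**Stronger readings a reader might infer.**
- *That the trial is underpowered.* The documents cannot show this. No MoCA SD or target difference is given, and three of the four SDs tabulated exceed the plan's 2.75, so the unadjusted column leans low by choice of illustration.
- *That S and δ were taken from a dementia study.* The plan attributes them to expert opinion with that citation beside them, and their origin cannot be checked. The literature review notes that psychomotor therapy has been studied mainly in dementia, which may explain borrowing.
- *That the arithmetic is wrong.* It is not.

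**Adjustment cannot repair a comparison of two institutions.** True, and the plan should say so. It is no reason to keep a test that makes no group comparison.

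**Conclusion.** The concern holds and should be corrected before analysis. The test mismatch is the main part: as written, the named test cannot answer Objective 3, whatever the values of SD and r. The percentages illustrating it rest on an assumed 1-point shared gain and SD 3.0.

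The power mismatch is secondary. β = 0.10 describes neither the stated outcome nor the stated test, so 90% power is unsupported for MoCA. The direction of the error is unknown, and the point does not by itself call for a different sample size.

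**What to change.** Keep 76.

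1. **Test.** In both the opening summary and section 11, replace the paired t-test as the test of effectiveness. Suggested text: *The effect on MoCA total score will be tested by ANCOVA of the week-12 score on group with baseline MoCA as covariate (two-sided 5%), reporting the adjusted between-group difference and 95% CI. Paired within-group changes are descriptive. The adjusted difference cannot be separated from differences between the two institutions.* Split the dummy tables by group, n = 38 each. Make the cognitive subscale rows match the appended MoCA form: rows such as Registration and Language and Praxis are not sections of that form.

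2. **Section 7.** Label S and δ as MMSE values used as a proxy. Replace the 90% power claim for the trial's outcome with the MoCA difference detectable at 34 evaluable per group: about 0.80 × SD with no credit for adjustment, or about 0.80 × SD × √(1 − r²) if a cited r is available. Note the increase of about 3% or 12% if the institutions differ at baseline by 0.5 or 1.0 SD. Cite the source of the MoCA SD, and say how the detectable difference compares with a MoCA difference considered worthwhile.

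3. **Editorial.** Change specific objective 2 to specific objective 3 in section 7.

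**Cost.** One sentence in each of two places, one paragraph in section 7, and the dummy-table rows and columns. No extra participants, visits or measurements are needed, since baseline MoCA is already collected. The restated figure may be less favourable than 90%, and the confounding of group with institution remains.
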